## Précis:

- *Objective.* The overall goal of this study is to determine the safety, tolerability, and radiological efficacy of up to 12 weeks of subcutaneous injection of anakinra in people with multiple sclerosis and evidence, by magnetic resonance imaging (MRI), of chronic active (also known as “smoldering”) lesions in the white matter.
- *Study population.* 5 people with progressive or stable MS, at least one paramagnetic rim lesion on 7-tesla MRI, and no new white matter lesion formation for at least 3 months or clinical relapse for at least 12 months, will complete the study.
- *Design.* In this open label, dose escalation study, participants will receive up to 12 weeks of subcutaneous anakinra with initial dose of 100 mg daily up to a target dose of 300 mg daily. Study visits will occur every 4 weeks while on treatment, with 2 follow-up visits at 4 and 12 weeks after treatment discontinuation.
- *Outcome measures.* The primary outcome measure is disappearance of one or more paramagnetic rims from white matter lesions identified at baseline. Secondary outcomes include safety and tolerability, clinical and radiological outcomes. Exploratory serological and CSF measures will also be obtained to investigate mechanism of action of anakinra and for biomarker development.

## List of Abbreviations

AE	adverse event
ANC	absolute neutrophil count
ALT	alanine aminotransferase
AST	aspartate aminotransferase
BBB	blood-brain barrier
CBC	complete blood count
CDC	centers for disease control and prevention
CNS	central nervous system
CSF	cerebrospinal fluid
DLT	dose-limiting toxicity
EAE	experimental allergic encephalomyelitis
E.coli	Escherichia coli
EDSS	Expanded Disability Status Scale
EGFR	estimated glomerular filtration rate
GVHD	graft versus host disease
HDS	human data sharing
IL	interleukin
IL-1	interleukin-1
IL-1 $\alpha$ -	interleukin-1 $\alpha$ (alfa)
IL-1 $\beta$ -	interleukin-1 $\beta$ (beta)
IL-1Ra	interleukin-1 receptor antagonist
rhIL-1ra	recombinant human interleukin-1 receptor antagonist
sIL-1R	soluble mouse recombinant interleukin-1 receptor
IP-10/CXCL10	interferon-gamma-induced protein 10/C-X-C motif chemokine 10
IND	investigational new drug
IFN $\gamma$	interferon gamma
IRB	institutional review board
IRIS	Integrated Research Information System
ISM	independent safety monitor
IV	intravenous
KDa	kilo Dalton
LP	lumbar puncture
MRI	magnetic resonance imaging
MS	multiple sclerosis
MSFC	MS Functional Composite
NOMID	Neonatal-Onset Multisystem Inflammatory Disease
NMR	nuclear magnetic resonance
OCT	ocular coherence tomography
PET	positron emission tomography

CNS IRB Protocol Template (5.4.17)

PMN .....	polymorphonuclear neutrophils
QA.....	quality assurance
RA .....	rheumatoid arthritis
SAE .....	serious adverse event
SC .....	subcutaneous
SDMT .....	Symbol Digit Modalities Test
T .....	tesla
TB .....	tuberculosis
TNF .....	tumor necrosis factor
TEAE .....	treatment-emergent adverse event
TUG .....	timed up-and-go
ULN .....	upper limit of normal
WHO .....	world health organization
9HPT .....	9-hole peg test

## 1. Introduction and Background

The purpose of this protocol is to test whether short-term treatment with anakinra, a recombinant, nonglycosylated form of the human interleukin-1 (IL-1) receptor antagonist (IL-1Ra), affects an imaging marker (the “paramagnetic rim”) associated with chronically inflamed (“chronic active” or “smoldering”) white matter lesions in multiple sclerosis (MS).

Section 0 begins with a general overview of the rationale for studying chronic active MS lesions and the advantages of approaching this study with ultra-high-field (7T) MRI. In Section 1.2, we discuss the role of IL-1 and microglia in chronic active lesions. Section 1.3 describes anakinra, Section 1.4 the study rationale, Section 1.5 the risks and benefits based on preclinical and prior clinical testing, and Section 1.6 the proposed dosing. Finally, Section 1.7 provides the rationale for our exploratory outcome measures.

### Rationale for studying chronic active MS lesions

MS is a chronic immune-mediated disorder of the brain, spinal cord, and optic nerves (1). Since the early 1980s (2), MRI has been recognized as a valuable tool for diagnosing and monitoring MS (3, 4). Moreover, the pathognomonic focal demyelinating plaques, also termed “lesions,” have been the subject of intense clinical and imaging research interest in MS.

It is widely accepted in the scientific community that newly forming demyelinating lesions are associated with inflammation and the short-term, abrupt opening of the blood-brain barrier (BBB) at the level of medium and small-caliber parenchymal veins (5). The imaging correlate of these changes is the leakage of a peripherally injected MRI contrast agent, usually gadolinium-based, into the parenchyma surrounding the inflamed venule. In our former studies, we were able to image this dynamic process at high resolution, and we termed it “centrifugal enhancement” (6, 7). We described subsequent changes in the BBB in capillaries and venules at the lesion’s leading edge as “centripetal enhancement” (previously termed “ring” or “rim enhancement” in non-dynamic MRI acquisitions) (6, 7).

The working hypothesis of the Translational Neuroradiology Section is that centripetal contrast enhancement is best considered as a manifestation of the immune response to focal inflammatory demyelination in new MS plaques. Metaphorically, this process can be thought of as a “controlled burn,” in which inflammation is used to counter inflammation as part of normal wound healing (8, 9). However, such controlled inflammation might also be detrimental. Indeed, we have evidence that inflammation of

this type can sometimes result in a persistent paramagnetic rim at the lesion edge, visualizable on MRI scans generated from the phase of the signal obtained via a T2\*-weighted gradient-echo pulse sequence at 7T (10). Persistent paramagnetic rims develop more commonly in lesions that form in older people age (Fig. 1) (11), consistent with laboratory data suggesting that inflammatory cell-mediated remyelination becomes progressively less successful with age (12, 13). Through our *in vivo* and postmortem investigations, we have found that paramagnetic-rim lesions are associated with extensive intralesional tissue damage (based on measurement of the T1 relaxation time by MRI), failed repair, apparently permanent demyelination, and iron deposition within activated macrophages/microglia (11). Further, we have shown that this lesion outcome is associated with a more pro-inflammatory peripheral blood cytokine and chemokine profile at baseline.

[figure not shown]

Figure 1. Semi logarithmic plot of the longitudinal volume for each lesion according to participant age and lesion group (centripetal with persistent paramagnetic rim and centripetal with transient paramagnetic rim) (Absinta et al., 2016b).

Over the past decade, results from several labs have converged to indicate that the pathological basis of the paramagnetic rim is in fact iron accumulation within activated macrophages/microglia, which is visible on 7T MRI (11, 14, 15). These rims can be long-lasting (16) (potentially for several decades), and pathologically they mark the class of chronically inflamed lesions known, variously, as “chronic active,” “slowly expanding,” or “smoldering.” Such lesions make up approximately 10–30% of white matter lesions in MS and are substantially more common in longstanding, clinically progressive disease (17). Pathologically, they show evidence of ongoing myelin destruction at the lesion edge, even in lesions that may have been present for decades. Stopping the adverse inflammation in such lesions, potentially opening the door for remyelination, is therefore an important treatment target, for which none of the existing MS drugs is known to be effective.

### Role of IL-1 in chronic active lesions in MS

IL-1 $\beta$  production is induced in response to inflammatory stimuli and mediates various physiologic responses, including inflammatory and immunological responses. Early *in vitro* studies showed that IL-1 $\beta$  in brain is produced mainly by ameboid microglia (18). In studies, evaluating postmortem brain material of MS patients, IL-1 was found to be expressed mostly by macrophages within the lesion center and by microglia at the lesion edge and beyond it (19, 20). More recent studies, using combined immunocytochemistry and *in situ* hybridization, confirmed the cellular source of IL-1 $\beta$  to be primarily microglia (21).

Further studies, showed, that the chronic expression of IL-1 leads to the recruitment of PMN to the brain parenchyma and induces the activation of microglia and astrocytes, BBB breakdown, and reversible demyelination (22).

In an animal model of MS (chronic relapsing experimental autoimmune encephalomyelitis), IL-1 $\beta$  and IL-1ra mRNA and protein were found in white and grey matter areas during early clinical phases of the disease. The cells, that expressed IL-1 $\beta$  and IL-1Ra mRNA, were macrophages or activated microglia (23).

Cerebrospinal fluid (CSF) analysis in MS has demonstrated elevated levels of members of IL-1 family, in particular IL-1 $\beta$  and IL-1Ra, with further elevations in IL-1Ra after high-dose corticosteroid therapy (24). Another study determined that detection of IL-1 $\beta$  in CSF correlated with higher cortical lesion volume and number, but there was no correlation with the presence of acute gadolinium-enhancing lesions (25).

In preclinical studies in EAE, injections of IL-1 $\alpha$  resulted in more severe disease, compared to controls. In addition soluble mouse recombinant IL-1R (sIL-1R), administered as an IL-1 antagonist, led to suppression of clinical paralysis and reduced wasting (26). Finally, IL-1 $\beta$  inhibition has not been previously investigated in MS, but, in subsequent studies, it was determined that intraventricular anakinra delays the repopulation of the microglia after their initial depletion (27). In addition, an early study with in vivo treatment with recombinant human IL-1 receptor antagonist (rhIL-1ra) showed suppression of clinical paralysis and reduction in level of wasting secondary to EAE, compared to control groups (28).

Since the paramagnetic rim of chronic active lesions in MS is due to iron accumulation within activated macrophages/microglia, and since IL-1 $\beta$  is produced mainly by microglia, we hypothesize that antagonization of IL-1 $\beta$  by anakinra could inhibit microglial proliferation and possibly lead to resolution of the chronic active lesions in MS. This would be detectable by elimination, or perhaps reduction, of the paramagnetic rim around such lesions.

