## 9. Outcome Measures

### Primary outcome measures

The primary outcome measure is the presence or absence of a paramagnetic rim around chronic active white matter MS lesions, assessed at the end of the dosing period.

Definition of efficacy endpoint: disappearance of one or all paramagnetic phase rims. At each study visit, paramagnetic phase rims will be assessed. For the purposes of dose escalation, if at any on-treatment scan, all paramagnetic rims that were present at baseline are no longer seen, dose escalation will end and the subject will proceed into the post-treatment follow-up phase of the study.

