## Secondary outcome measures

- Safety and tolerability: AE tables
- Clinical
  - Expanded Disability Status Scale (EDSS)
  - 9-hole peg test (9HPT)
  - Symbol digit modalities test (SDMT)
- MRI:
  - Proportion of paramagnetic rim lesions in which the rim has diminished or disappeared at any time point
  - Changes in T1 relaxation time within paramagnetic rim lesions at all time points, relative to non-rim lesions
  - Changes in size of paramagnetic rim lesions at all time points, relative to non-rim lesions

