## Exploratory outcome measures

Exploratory outcome measures will be derived from clinical scales (may include those mentioned as secondary outcome measures and others, e.g. 25-foot timed walk, paced auditory serial addition test, and Scripps Neurological Rating Scale), MRI parameters ((characteristics/persistence of paramagnetic rims at all time points (qualitative)), and stored biofluids, with focus on immune cell populations (e.g. macrophages, lymphocytes, and subtypes thereof), cytokines (e.g., IL-1 $\beta$ , IL-1Ra, IL-6), and also on protein and other biomarkers of neurodegeneration (e.g. neurofilament light chain). Additional assays (e.g. for anti-anakinra antibodies) may also be performed. These analyses will be performed in NIH labs or through collaboration, either intramural or extramural.

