## 10. Statistical Analysis

### Analysis of data/study outcomes

The primary outcome is the per-patient proportion of lesions in which the paramagnetic rim has been modulated at the end of the dosing period. Proportion of diminished/resolved paramagnetic rims will be analyzed by investigators blinded to time point, reported descriptively, and compared to the assumption of no change off therapy (11, 16) — a reasonable assumption since we have never observed complete disappearance of a chronic rim — via Binomial exact tests.

For the secondary outcome measures, safety and tolerability will be assessed qualitatively; AEs will be tabulated and compared to prior published and unpublished (to the extent possible) data on anakinra. Quantification will include the proportion of participants who start anakinra therapy and complete the full dosing. MRI outcomes will be reduced to scalar measures at various time points. Longitudinal changes in rim presence/absence, T1 relaxation time, and lesion volume will be analyzed by analysis of variance or mixed-effects models (which naturally handle missing data), the latter two in comparison to

CNS IRB Protocol Template (5.4.17)

non-rim lesions. Analyses will be performed both in completers and on an intent-to-treat basis. There will be no interim analysis.

Analysis methods for exploratory outcome measures will be determined by the study team and collaborators at a later time point.

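### Partial rim change is part of the hypothesis, but it is only counted in an undefined category pooled with disappearance, and Sections 9 and 10 disagree on whether it counts in the primary outcome

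*Combined protocol and SAP*

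**What the plan says.** Section 1 (Role of IL-1 in chronic active lesions in MS) names two forms of effect: "This would be detectable by elimination, or perhaps reduction, of the paramagnetic rim around such lesions". The same section describes the rim as a finding "visualizable on MRI scans generated from the phase of the signal" of a gradient-echo sequence at 7T.

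The rim outcomes are then as follows.

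- Section 9, primary: "The primary outcome measure is the presence or absence of a paramagnetic rim around chronic active white matter MS lesions". The section continues: "Definition of efficacy endpoint: disappearance of one or all paramagnetic phase rims".
- Section 9, secondary: "Proportion of paramagnetic rim lesions in which the rim has diminished or disappeared at any time point".
- Section 9, exploratory: rim characteristics and persistence, labelled qualitative.
- Section 10, primary: "The primary outcome is the per-patient proportion of lesions in which the paramagnetic rim has been modulated at the end of the dosing period". The next sentence counts diminished and resolved rims together, read by investigators blinded to time point, and takes them to exact binomial tests.
- Section 10, longitudinal models: "Longitudinal changes in rim presence/absence, T1 relaxation time, and lesion volume will be analyzed by analysis of variance or mixed-effects models".

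The Power analysis uses five participants and a null rate of 0.01, and rejects if one person has at least one lesion change.

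**The concern.** There are two linked gaps.

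First, nothing records by how much a rim has weakened. Diminished and modulated have no threshold, grading scale or reader-agreement plan, and each is reported together with complete disappearance. T1 and lesion volume are numeric, but they describe the lesion. The rim, which is the treatment target, has no numeric measure of its own.

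Second, the primary outcome has two definitions. Under Section 9, a drug that weakens every rim and abolishes none yields no responders. Under Section 10, the same result could count in every participant. The choice also determines which null rate is relevant. Section 10 supports the no-change assumption by the absence of any observed complete disappearance, which says nothing about weakening. The Power analysis itself reports subtle change in 1 of 29 untreated people.

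**Working it through.** **1. The plan's own figure.** Inputs from the Power analysis: n = 5, null 0.01, difference 0.27 (so alternative 0.28), reject at one or more of five.

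- Type I error = 1 − 0.99^5 = 0.0490.
- Power = 1 − 0.72^5 = 0.8065, so the stated 80% reproduces.
- The largest null rate that keeps the level at 0.05 is 1 − 0.95^(1/5) = 0.0102. The rule has almost no slack above 0.01.

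**2. The same rule if diminished rims count.** Level = 1 − (1 − p0)^5, where p0 is the untreated per-participant rate.

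| p0 | Source | Level |
|---|---|---|
| 0.01 | Power analysis | 4.9% |
| 0.02 | assumed, in between | 9.6% |
| 1/29 = 0.0345 | subtle change over several years, Power analysis | 16.1% |

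The last row is an upper-end value, because dosing lasts at most 12 weeks.

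**3. What a count loses against a measurement.** The documents give no SD for a numeric rim measure, so work in SD units. Assume that each participant's mean rim change is normal and shifted by d SD.

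- Count: a participant is a responder beyond the cut-off whose null rate is 0.01 (2.326 SD). Then p = 1 − Φ(2.326 − d), and power = 1 − (1 − p)^5.
- Measurement: one-sided paired t-test at 0.05, 4 df, critical value 2.132, noncentrality d√5.

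| d | p | Power, count | Power, t-test |
|---|---|---|---|
| 0.5 | 0.034 | 16% | 24% |
| 1.0 | 0.092 | 38% | 58% |
| 1.36 | 0.167 | 60% | 80% |
| 1.5 | 0.204 | 68% | 86% |
| 2.0 | 0.372 | 90% | 97% |

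**4. A threshold to avoid.** One tempting definition calls a rim diminished when its fall on treatment exceeds its own change between a prior scan and baseline. Assume no drug effect and independent normal scan errors of equal size. A fall then exceeds the signed prior change with probability 0.5 and the absolute prior change with probability 0.25. With one rim in each of five people, the one-event rule rejects falsely with probability 1 − 0.5^5 = 0.97 or 1 − 0.75^5 = 0.76. A single noisy difference cannot serve as a threshold.

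**The case against.** A reader might infer that the trial cannot detect partial change at all, or that a partial effect leaves the test with 4.9% power where a continuous measure would have 86%. The documents do not support either reading. The secondary outcome counts diminished rims, Section 10 puts them into the exact test, and the Power analysis rejects on any one lesion change. The 4.9% applies only if the Section 9 definition governs and no rim disappears. Compared like for like, the gap is about 20 points (58% against 38% at 1.0 SD; 86% against 68% at 1.5 SD).

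Four further points can be made for the plan.

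- Readers are blinded to time point. This addresses optimism bias, but it sets no threshold and does not remove random reading error.
- Section 10 says that MRI outcomes will be reduced to scalars. This leaves room for a rim measure, but the rim scalar it goes on to name is presence or absence.
- The Power analysis starts from 1 in 29 and expects few or no changes over a shorter period. A rate below 1/29 is reasonable, but the step to 0.01 is not derived, and a null of 0.02 already gives 9.6%.
- This is an open-label pilot with five completers, and the documents give no test-retest error for a numeric rim measure. That is a good reason to make such a measure secondary and not primary. It does not justify leaving the size of the effect unmeasured.

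The method of reading rims is not described, so it is an inference that the calls are purely visual.

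**Conclusion.** The concern holds in this form: partial change in the rim is counted and tested but not quantified, its category is undefined, and Sections 9 and 10 give different answers on whether it belongs to the primary outcome.

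If diminished rims count, the type I error of the one-event rule runs from 4.9% at the planned null to 16.1% at 1/29. The true 12-week rate is unknown and probably lies below 1/29. If only disappearance counts, the 4.9% stands on the plan's assumed null, but the reduction named in the hypothesis is left to a pooled, undefined category.

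The gain from a numeric measure is about 20 points of power at mean changes of 1.0 to 1.36 SD. It rests on an assumed normal model and on an SD that the documents do not supply, so it is illustrative. Even with a numeric measure, 80% power in five people needs a mean change of 1.36 SD. Its main value is an estimate with an interval.

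**What to change.** 1. Keep disappearance (presence or absence at the end of dosing) as the primary outcome, and reword Section 10 and the rejection rule in the Power analysis to match. The null rate and the event then refer to the same thing.
2. Add one prespecified secondary outcome to Sections 9 and 10, taken from the 7T phase images used to identify rims. For each baseline rim, take the signal in the rim minus that in adjacent perilesional white matter, on regions drawn at baseline and registered to later scans. Average within participant. Report the change from baseline to the end of dosing with a paired confidence interval, with participants as the unit (n = participants).
3. Report diminished rims descriptively and separately from disappeared rims. Do not define diminished by a single prior-to-baseline difference. Besides the error rates above, a separate comparable scan is not assured: the inclusion criteria ask for a prior 7T scan without a date or sequence, and the baseline procedures allow screening data to serve as baseline.

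The cost is SAP wording and image post-processing, with no new visit or scan. There are limits. Test-retest error is unknown. It is an inference that suitable phase data will be acquired, because the sequences are not listed and acquisition parameters may be modified. Visits at which a 3T scan substitutes (Section 4, Study overview) may not contribute.

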## Anakinra

Anakinra is a recombinant, nonglycosylated form of the human interleukin-1 (IL-1) receptor antagonist (IL-1Ra), produced by recombinant DNA technology using an *E. coli* bacterial expression system. Anakinra consists of 153 amino acids and has a molecular weight of 17.3 kDa. Anakinra belongs to the pharmacological class of IL-1 inhibitors: it blocks the biological activity of IL-1 $\beta$  by competitively inhibiting IL-1 $\beta$  binding to the interleukin-1 type I receptor (IL-1RI), expressed in a wide variety of tissues and organs. Anakinra is FDA-approved for use in rheumatoid arthritis (RA) and the cryopyrin-associated periodic syndrome Neonatal-Onset Multisystem Inflammatory Disease (NOMID) (29).

### *Pharmacokinetics:*

The absolute bioavailability of anakinra after a 70-mg subcutaneous (SC) bolus injection in healthy individuals (n=11) is 95%. In people with RA, maximum plasma concentrations of anakinra occurred 3–7 CNS IRB Protocol Template (5.4.17)

hours after SC administration of anakinra at clinically relevant doses (1 to 2 mg/kg; n=18); the terminal half-life ranged from 4–6 hours. In RA patients, no unexpected accumulation of anakinra was observed after daily SC doses for up to 24 weeks.

The estimated anakinra clearance increases with increasing creatinine clearance and body weight, as established in the pharmacokinetic analysis encompassing 341 patients receiving daily SC anakinra injection at doses of 30, 75, and 150 mg for maximum of 24 weeks (29). In individuals with severe or end stage renal disease, the mean plasma clearance of Anakinra decreased by 70–75%. In patients with hepatic impairment, no formal studies have been conducted.

Five clinical studies of anakinra in treatment of rheumatoid arthritis, with a total of 3055 patients, have been conducted. Collectively, these studies have shown significant improvement in clinical, laboratory, and radiographic parameters in the treated groups, although there was no additional benefit of anakinra in combination with a TNF inhibitor, etanercept (30–34). Safety data from these trials show that anakinra has been generally well-tolerated, with no difference in serious adverse events (SAEs) compared to placebo group. Concurrent administration of anakinra and etanercept for up to 24 weeks resulted in a 7% rate of serious infections, vs. 0% in the etanercept-only group (0%); 2% of the concurrent therapy group patients developed neutropenia (absolute neutrophil count <10^9/L) (32, 34). Therefore, use of anakinra combined with a TNF-blocking agent is not recommended.

Anakinra has also been approved by the FDA for treatment of neonatal onset multisystem inflammatory disease (NOMID), having produced improvement in neurological and systemic manifestations of disease, correlating with improvement in laboratory parameters; indeed, most NOMID patients have achieved sustained disease control (35). Further evidence suggests a benefit of IL-1 $\beta$  inhibition in other autoimmune disorders, including Schnitzler's syndrome, Behçet's disease, adult-onset Still disease, systemic juvenile idiopathic arthritis, gout, etc. (36).

